Colitis, Grade 3	
 
Withhold atezolizumab, idasanutlin and cobimetinib.
 
Initiate supportive care and monitor patient closely.
 
Discontinue medications that may exacerbate colitis (e.g., NSAIDS).
 
Refer patient to gastrointestinal specialist for evaluation and confirmatory biopsy.
 
Initiate treatment with 1- 2 mg/kg/day IV methylprednisolone or equivalent and convert to 1- 2 mg/kg/day oral prednisone or equivalent upon improvement.
 
If event resolves to Grade 1 or better within 12 weeks, resume atezolizumab at fixed dose. If not, permanently discontinue atezolizumab, cobimetinib and idasanutlin
 
If event resolves to Grade 1 or better within 28 days, resume cobimetinib with dose reduced by one level. If not, permanently discontinue cobimetinib and idasanutlin.
 
		

 
Permanently discontinue atezolizumab, idasanutlin and cobimetinib, and contain Medical Monitor.
 
Initiate supportive care and monitor patient closely.
 
Discontinue medications that may exacerbate colitis (e.g., NSAIDS).
 
Refer patient to gastrointestinal specialist for evaluation and confirmatory biops.
 
Initiate treatment with 1- 2 mg/kg/day IV methylprednisolone or equivalent and convert to 1- 2 mg/kg/day oral prednisone or equivalent upon improvement.
 
If event does not improve within 48 hours after initiating corticosteroids, considerable adding an immunosuppressive agent.
 
If event resolves to Grade 1 or better, taper corticosteroids over 1 month.
 
			

Nausea and Vomitino	g (Cobimetinib or Idasanutlin)				
	Continue Cohimetinih or Idasanutlin at same doses				
Grade 1 / 2	Begin maximum supportive care and adequate anti-emetic treatments				
Grade 3 / 4	Begin maximum supportive care and adequate combination anti-emetic treatments, including ondansetron and aprepitant.  May delay Cobimetinib or Idasanutlin dosing (up to 28 days) until Grade ≤ 1 on maximum supportive care and then restart but decrease dose one level.  Permanently discontinue if after restarting, the patient experiences persistent nausea and/or vomiting despite prophylaxis and treatment requiring need to withhold treatment.				
Pancreatic toxicity (A	Atezolizumab)				

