Amylase or lipase elevation, Grade 3 or 4	
 
Withhold Atezolizumab.
 
Resume Atezolizumab if event resolves to Grade 1 or better within 12 weeks
 
Permanently discontinue Atezolizumab if event does not resolve to Grade 1 or better within 12 weeks
 
For recurrent events, permanently discontinue Atezolizumab
 
				
Immune-related pancreatitis, Grade 2 or 3	
 
Withhold Atezolizumab
 
Resume Atezolizumab if event resolves to Grade 1 or better within 12 weeks
 
Permanently discontinue Atezolizumab if event does not resolve to Grade 1 or better within 12 weeks
 
For recurrent events, permanently discontinue Atezolizumab
 
				
Immune-related pancreatitis, Grade 4	Permanently discontinue Atezolizumab.				
Skin and subcutaned	ous (Cobimetinib or Atezolizumab)				
General guidance	A dermatologist should evaluate persistent and/or severe rash or pruritus. A biopsy should be considered unless contraindicated.				

 
Continue atezolizumab and cobimetinib.
 
Initiate supportive care (e.g., antihistamines, topical corticosteroids). If event do not improve, consider treatment with higher-potency topical corticosteroids.
 
For grade 2 rash, consider referral to dermatologist.
 
Acneiform rash:
 
Consider topical corticosteroids (e.g., hydrocortisone 2.5%, alclometasone) an antibiotics (minocycline, doxycycline, or antibiotics covering skin flora) as clinic indicated.
 
					

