Dermatologic event, Grade 3	
 
Withhold atezolizumab and cobimetinib.
 
Refer patient to dermatologist. A biopsy should be performed if appropriate.
 
Consider initiating treatment with 10 mg/day oral prednisone or equivalent, increasing dose to 1–2 mg/kg/day if event does not improve within 48–72 hours.
 
If event resolves to Grade 2 or better within 12 weeks, resume atezolizumab at fixed dose. If not, permanently discontinue atezolizumab and cobimetinib
 
Permanently discontinue atezolizumab and cobimetinib and contact Medical Monitor if event does not resolve to Grade 1 or better within 12 weeks.
 
If event resolves to Grade 2 or better within 28 days, resume cobimetinib with dose reduced by one level. If not, permanently discontinue cobimetinib.
 
Acneiform rash:
 
Consider continuation of topical corticosteroids (e.g., 2.5% alclometasone) and oral antibiotics (e.g., minocycline, doxycycline or antibiotics covering skin flora) when restarting cobimetinib.
 
			
Dermatologic event, Grade 4	Permanently discontinue atezolizumab and cobimetinib, and contact Medical Monitor.			
General (Cobimetinil	o or Idasanutilin)			
Fatigue/ asthenia				
Grade 1 / 2	Maintain dose level of Cobimetinib or Idasanutlin.			
Grade 3	Omit dose of Cobimetinib of Idasanutlin.  Omit dose of Cobimetinib or Idasanutlin until resolved to CTCAE Grade ≤ 1, then  - If resolved in ≤ 7 days, maintain dose level of Cobimetinib or Idasanutlin.  - If resolved in > 7 days, discontinue patient from Cobimetinib or Idasanutlin.			
Neurologic (Atezoliz	umab)			
Immune-related neuropathy, Grade 2	
 
Withhold Atezolizumab.
 
Resume Atezolizumab if event resolves to Grade 1 or better within 12 weeks
 
Permanently discontinue Atezolizumab if event does not resolve to Grade 1 or better within 12 weeks
 
			
Immune-related neuropathy, Grade 3 or 4	Permanently discontinue Atezolizumab			
Myasthenia gravis and Guillain-Barré, all grades	Permanently discontinue Atezolizumab			
Immune-related meningoencephalitis, all grades	Permanently discontinue Atezolizumab			
Other AEs				
Grade 1 / 2 Grade 3	Maintain dose level of Atezolizumab, Cobimetinib or Idasanutlin  Omit dose of Atezolizumab, Cobimetinib or Idasanutlin until resolved to CTCAE Grade  ≤ 1 within 28 days, then ↓ dose level of Cobimetinib. If adverse event persists > 28  days, permanently discontinue Cobimetinib or Idasanutlin			

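### Grade 3 skin row, section 8.5: an event whose best grade by week 12 is Grade 2 meets both a resume and a permanent-stop instruction for atezolizumab

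*Combined protocol and SAP*

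**What the plan says.** The skin and subcutaneous block of section 8.5 is headed "Cobimetinib or Atezolizumab". Its Grade 3 row withholds both drugs and then gives three recovery rules:

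- Atezolizumab: "If event resolves to Grade 2 or better within 12 weeks, resume atezolizumab at fixed dose". The same bullet goes on: "If not, permanently discontinue atezolizumab and cobimetinib".
- Both drugs: "Permanently discontinue atezolizumab and cobimetinib and contact Medical Monitor if event does not resolve to Grade 1 or better within 12 weeks".
- Cobimetinib: "If event resolves to Grade 2 or better within 28 days, resume cobimetinib with dose reduced by one level", with a permanent cobimetinib stop if that is not met.

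The row does not say when the 12-week and 28-day windows start, or how the first two bullets relate to each other.

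**The concern.** The first two bullets concern the same event, the same drugs and the same 12-week limit, but they set different recovery grades. A site whose patient has improved from Grade 3 to Grade 2, and no further, is told by one bullet to restart atezolizumab and by the next to end both drugs permanently.

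What is at stake is whether that patient stays on treatment. Section 8.6 takes a patient off both study drugs once atezolizumab is permanently stopped for toxicity. The row also reaches beyond the cobimetinib arm: the block covers atezolizumab, which idasanutlin-arm patients receive as well.

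**Working it through.** No arithmetic applies, so the check is to run the rules against every possible outcome and then look for a tie-breaker.

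**1. Outcomes.** Let g be the best grade reached by week 12. The first bullet says resume if g ≤ 2 and stop if g ≥ 3. The second says stop if g ≥ 2.

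| Best grade by week 12 | First bullet | Second bullet | Result |
|---|---|---|---|
| 1 or better | Resume | No stop | Consistent |
| 2 | Resume | Permanent stop | Conflict |
| 3 or worse | Permanent stop | Permanent stop | Consistent |

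Grade 2 is the only conflicting outcome.

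**2. Can the bullets be read in sequence?** Suppose a site restarts at Grade 2 and stops later if Grade 1 is not reached by week 12. For a patient who reached Grade 2 early, that can be followed. But any event with g ≥ 3 also has g ≥ 2, so the second bullet already stops it, and the first bullet's own stop clause does no work. If Grade 2 is first reached close to week 12, the restart and the permanent stop fall almost together.

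**3. Does another section decide it?**
- Section 7.6 (idasanutlin arm) answers Grade 2 or worse skin toxicity lasting more than 28 days with dose reduction. Section 8.5 allows no atezolizumab dose reduction, so this does not help.
- Section 8.4.2 generally continues atezolizumab through Grade 1 to 2 immune-related events. It gives no rule for recovery from Grade 3.
- Section 8.4.2.4, on dermatologic toxicity, gives no recovery grade.
- The general atezolizumab rules in section 8.5 set a steroid taper, a 12-week limit on holds, and conditions for resumption after full recovery. They rank neither bullet.
- Section 8.6 requires modifications of the guidelines to be discussed with the Principal Investigator in advance. It does not say which guideline applies.

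**4. Which grade was intended?** The evidence divides.
- For Grade 2: the cobimetinib bullet in the same row uses it. The preceding skin row continues both drugs, and its text includes Grade 2 rash ("For grade 2 rash, consider referral to dermatologist").
- For Grade 1: most other atezolizumab rows use it. Grade 3 colitis has "If event resolves to Grade 1 or better within 12 weeks, resume atezolizumab at fixed dose". The amylase/lipase and pancreatitis rows pair a Grade 1 resume rule with "Permanently discontinue Atezolizumab if event does not resolve to Grade 1 or better within 12 weeks". Grade 2 pneumonitis, diarrhea and Grade 2 neuropathy also use Grade 1. The general resumption rule in section 8.5 speaks of full recovery.

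**5. Consequence by arm.**
- Cobimetinib arm, Grade 2 reached within 28 days: cobimetinib restarts one level down (60 to 40 mg in the section 8.5 table). The second bullet would later stop both drugs if the event never reached Grade 1.
- Cobimetinib arm, Grade 2 first reached after 28 days: the row's cobimetinib bullet stops cobimetinib anyway. Whether atezolizumab may continue alone then depends also on the rules for delays over 28 days (sections 7.11 and 8.5) and on the single-agent allowance in section 8.6.
- Idasanutlin arm: the row governs atezolizumab only, but stopping it permanently ends both drugs under section 8.6.

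**6. Size.** Section 24.3.1 allows at most 33 patients per arm in phase II, so the row could apply to 33 + 33 = 66 patients. Phase Ib patients also receive atezolizumab. This counts patients to whom the row could apply, not patients expected to meet the conflict. For cobimetinib with atezolizumab, section 3.7.1.7 gives all-grade rates of 43.5% for dermatitis acneiform and 34.8% for rash, but no Grade 3–4 skin total. It names diarrhea as the only treatment-related Grade 3–4 event seen in two or more patients. The protocol gives no skin rate for idasanutlin with atezolizumab, and no rate for Grade 3 events that settle at Grade 2. A count cannot be derived.

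**The case against.** The strongest reply is that the row says resume, which is a single action, and never says continue. A patient who restarted at Grade 2 has already carried out the first bullet, so at week 12 only the second bullet has anything left to do. The row can then be followed in order. This stands in part: a reader might infer that every early restart leaves the site under two opposing orders, and the wording does not support that. But the row does not state the sequence, the sequence makes a written stop clause redundant, and it does not help when Grade 2 is first reached near the deadline.

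The second reply is that there are safeguards. The stop bullet calls for contact with the Medical Monitor. Section 8.6 treats the table as guidelines that can be modified with prior approval. Section 8.5 allows resumption of atezolizumab after full recovery, with approval documented by the investigator and the Medical Monitor. These make a silent difference between sites less likely. They do not say which bullet a site should apply.

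A reader might also infer that the Grade 1 bullet is a drafting remnant. The cobimetinib bullet and the preceding skin row make that tempting, but Grade 1 is the usual recovery grade in the other atezolizumab rows, so the documents do not establish it.

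**Conclusion.** The contradiction is real, confined to one outcome (best grade by week 12 equal to 2), and minor. It rests on the wording of two adjacent bullets and on finding no rule of precedence elsewhere. The intended grade cannot be recovered from the documents.

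Two further inferences should be resisted. One is that the stop bullet would end a restart that had already run for some fixed number of cycles. The row gives no start for either window. The general rules in section 8.5 count atezolizumab holds from the scheduled infusion and cobimetinib delays from the intended next dose. Where steroids were started for an atezolizumab-related toxicity, they must be tapered over at least one month before atezolizumab resumes. No duration can be stated. The other is that the trial's results are at risk: the number affected is unknown and probably small, and nothing here shows an effect on PFS, sample size or error rates.

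**What to change.** The sponsor's clinical team should choose one recovery grade for the row and edit it to match:

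- (a) Grade 2: delete the Grade 1 stop bullet. The first bullet already says what to do if Grade 2 is not reached.
- (b) Grade 1: change the atezolizumab and cobimetinib resume thresholds to Grade 1, as in the Grade 3 colitis row, and remove the stop clause that is then duplicated.

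If a restart at Grade 2 with a permanent stop at week 12 for events that never reach Grade 1 was intended, write that sequence out and state when the 12 weeks begin.

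The cost is amendment wording in one table row. Design, sample size and analysis do not change.

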# 8.6. Special Considerations

- For toxicities which are considered by the treating investigator unlikely to develop into serious or life-threatening events (e.g. alopecia, altered taste etc.), treatment may be continued at the same dose without reduction or interruption.
- The treating investigator may reduce a subject's dose for a toxicity of any grade/duration where s/he believes it to be in the best interests of the subject.
- Any consideration to modification of the above dose modification guidelines should be discussed with the Principal Investigator for approval or disapproval in advance.
- □ If a toxicity requiring Cobimetinib or Idasanutlin permanent drug interruption occurs, Atezolizumab can be continued as a single-agent
- ☐ If a toxicity requiring Atezolizumab permanent drug interruption occurs, patients will come off both study drugs

# Diagnostic Criteria and Recommended Management for Systemic Immune Activation

(applicable only when alternative etiologies have been excluded)				
Major Criteria	Minor Criteria			

 
Fever ≥ 38.5°C on more than one occasion
 
Ferritin ≥ 3000 ng/mL
 
Cytopenias (Grade ≥ 2 in two or more lineages)
 
	
 
Splenomegaly
 
Hemophagocytosis in bone marrow, spleen, or lymph nodes
 
Elevated GGT or LFTs (AST, ALT, or total bilirubin)
 
			

 
Age-adjusted soluble IL-2 receptor elevated by ≥ 2 standard deviations
 
Severe dysfunction in two or more organs
 
Decreased fibrinogen
 
	

Elevated triglycerides

Elevated LDH

Decreased natural killer cell activity

			

# **Diagnosis and Management of Systemic Immune Activation**

Number of Criteria	Diagnosis	Action to Be Taken	
≥ 4 major criteria	Consistent with systemic immune activation	
 
Permanently discontinue atezolizumab.
 
Consider treatment with an immunosuppressive agent (i.e., tocilizumab, infliximab, cyclosporine A, or etoposide) and IV corticosteroids (i.e., methylprednisolone 1 g once daily or equivalent).
 
Consider HLH-94 protocol if there is no clinical improvement.
 
	
3 major criteria OR 2 major plus ≥ 3 minor criteria	Probable systemic immune activation	Depending on clinical severity, follow guidelines for "Consistent with systemic immune activation" or "Possible systemic immune activation" diagnosis.	
2 major plus ≤ 2 minor criteria OR 1 major plus ≥ 4 minor criteria	Possible systemic immune activation	
 
Withhold atezolizumab.
 
Consider treatment with IV corticosteroids.
 
Follow guidelines for "Consistent with systemic immune activation" diagnosis if there is no clinical improvement or if clinical worsening occurs.
 
If clinical improvement occurs, atezolizumab may be resumed following a benefit-risk assessment.
 
	

## 9. DRUG FORMULATION/STORAGE/SUPPLY

## 9.1. Cobimetinib

#### 9.2. Supply

Cobimetinib is an investigational agent and will be supplied free-of-charge from Genentech.

#### 9.2.1. Formulation

The 20-mg Cobimetinib drug product is a film-coated, immediate release tablet. The white tablet is round with the engraving "ROCHE" on one side. Cobimetinib will be packaged in both bottles and blister packs. The inactive ingredients in Cobimetinib are as follows: lactose monohydrate. microcrystalline cellulose, croscarmellose sodium, and magnesium stearate for the tablet core. The tablet coating consists of polyvinyl alcohol-part hydrolyzed, titanium dioxide, polyethylene glycol 3350, and talc. For further details, see the Cobimetinib Investigator's Brochure.

## 9.2.2. Dosage, Administration, and Storage

Cobimetinib should not be stored above 25°C (77°F). If study drug is stored outside of the permitted temperature ranges, quarantine the affected supply and contact the Coordinating Center (who will contact Genentech, the drug supplier). The dose level of Cobimetinib to be tested in this study is 60 mg PO by self-administration daily on days 1 – 21 of each cycle, every 28 days.

## 9.3. Idasanutlin

## 9.3.1. Supply

Idasanutlin is an investigational agent and will be supplied free-of-charge from Genentech.

## 9.3.2. Formulation

The 50 mg, 200 mg, 300 mg, and 400 mg film-coated tablets with idasanutlin (SDP) that have been optimized for use in current and future studies and as market formulation contain the excipients copovidone, microcrystalline cellulose, croscarmellose sodium, crospovidone, colloidal silicon dioxide, magnesium stearate, and a film coat. The film coat of the 50 mg as well as 200 mg tablets consists of polyvinyl alcohol, titanium dioxide, polyethylene glycol, talc, iron oxide yellow, iron oxide red, and iron oxide black. The film coat of the 300 mg dose strength consists of polyvinyl alcohol, titanium dioxide, polyethylene glycol, and talc. The film coat of the 400 mg dose strength consists of polyvinyl alcohol, titanium dioxide, polyethylene glycol, talc, and iron oxide yellow.

## 9.3.3. Dosage, Adminitration, and Storage

Idasanutlin should not be stored above 25°C (77°F). The dose levels of Idasanutlin to be tested in this study are 300 - 500 mg PO by self-administration daily on days 1 – 5 of each cycle, every 28 days.

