### 3.7.2.7 Dose rationale for this study

Based on the new SDP formulation, all ongoing and future studies of idasanutlin will utilize the SDP formulation, which corresponds to 50% of the older MBP formulation. Therefore, the MTD for solid tumors on the 5 day schedule was 500 mg daily on the original formulation, and 250 mg of the current SDPformulation. Therefore, the doses tested in this study will range from 50 - 200 mg from D1 - 5 of each 28-day cycle.

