## 7.4.3 Idasanutlin

Patients will receive and self-administer Idasanutlin at (TBD) mg PO daily, on Days 1 – 5 of a 28days cycle.

Patients will be given a sufficient number of tablets to last until the next visit. In some cases, extra tablets may be dispensed if there is a possibility that the patient's next visit may be delayed (e.g., due to holiday, inclement weather, or distance of patient's home from study center).

Study drugs should be taken at approximately the same time each day, preferably in the morning, and no earlier than 1 hour and no later than 4 hours after the scheduled time. Each dose of Idasanutlin should be taken with a glass of water. Idasanutlin may be dosed with or without food. Idasanutlin tablets should never be chewed, cut, or crushed.

If a dose is missed (i.e., not taken within 4 hours after the scheduled dosing time), the patient should resume dosing with the next scheduled dose. Missed or vomited doses will not be made up. These events should be noted in the medication diary.

Patients will be asked to record the time and date they take each dose in a medication diary (located in the supplemental packet). Patients will also be given instructions for selfadministration as to the number and strength of the tablets to take. Patients will be instructed to bring all unused tablets and their medication diary to each study visit for assessment of compliance and medication disposal.

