# 7.6. Definition of Maximum Tolerated Dose (MTD) – for patients on idasanutlin arm only

The MTD will be defined as the highest dose tested in which a DLT is experienced by 0 out of 3 or 1 out of 6 patients among the dose levels. The first cohort of patients (3 patients) will be started at dose level 1, and each patient will be observed for 6 weeks on the specified dose:

If no patient in the first cohort of 3 experiences a DLT, accrual will continue to test the next dose level
If 1 patient experiences a DLT any given cohort/ dose level, an additional cohort of 3 patients will be treated at the same dose level
If 1 patient has a DLT out of 6 patients treated at this same dose, accrual will continue to test the next dose level
If 2 or more patients in 3 or 6 patients treated at a given dose experience DLT, the dose will be de-escalated to the next lower dose level. If the current dose level is at -1, the regimen will be considered too toxic and the corresponding cohort within the study will be discontinued
If 0 out of 3 or 1 out of 6 patients has a DLT treated at dose level 3, accrual will continue to the phase II portion of the study

No new cohort of patients will be treated until the previous cohort has been fully evaluated for toxicity and a dose escalation decision has been made. Routine updates regarding patient and study status will be conducted.

Once the MTD is reached, the expansion component of the study will be completed to assess tolerability and efficacy. Patients in the phase II portion of the study will initiate study treatment at the MTD defined in the escalation component of the trial. Note that dose reduction within patients (individually) is allowed after the 4 week DLT observation period in the escalation and in the expansion components of the study (see Dose Modification guidelines, Section 8). Intrapatient dose escalation will not be allowed. Dose reduction will be required for a given patient in case of:

- ☐ Grade 3 or 4 toxicities
- Grade ≥ 2 elevation of creatinine, bilirubin, AST, or ALT lasting more than 14 days despite medical treatment, or
- Grade ≥ 2 ocular, skin or nail toxicity for more than 28 days in a row despite optimal medical treatment, or
- Grade ≥ 2 GI toxicity lasting more than 14 days despite medical treatment.

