#### Phase Ib Trial of Idasanutlin and Atezolizumab 24.1.

For the dose-escalation study, a standard 3 + 3 dose escalation scheme will be utilized to evaluate the primary objective of determining a RP2D (Recommended Phase II Dose) for Idasanutlin in combination with Atezolizumab. Three dosing cohorts of Idasanutlin will be evaluated in combination with Atezolizumab (dosage will be held constant at 840 mg) to determine the RP2D and will occur in accordance with the dose escalation rule below.

1 Cycle = 28 days			
N of pts.	Dose Level	Atezolizumab (IV q15 days)	Idasanutlin (PO daily x 5 out of 28 days)
3-6	3	840 mg	200 mg
3-6	2	840 mg	150 mg
3-6	1	840 mg	100 mg
3-6	-1	840 mg	50 mg

DLTs are defined in section 7.5 and will be assessed during a DLT assessment window, which is during the first cycle of therapy. The RP2D from this study will be utilized in the Idasanutlin +

Atezolizumab arm in the Phase II portion of this study. The determination of the MTD and RP2D are reviewed in the following table. Of note, the PI may adjust the RP2D based on overall tolerability after cycle 1 at their discretion after discussion with all study Pl's.

Number of Patients with DLT at a given dose level	Escalation Decision Rule
0 out of 3	Enter 3 patients at the next dose level.  If dose level 3 is reached without DLT, then dose level 3 will be considered the MTD and RP2D.
>= 2	Dose escalation will be stopped. This dose level will be declared the maximally administered dose (highest dose administered), exceeding the MTD. Three (3) additional patients will be entered at the next lowest dose level if only 3 patients were treated previously at that dose.
	If this occurs at dose level 1, then 3-6 additional patients will be enrolled on dose level -1, based on toxicity occurring at that dose level. If ≥ 2 patients experience DLT at dose level -1, then the study is considered a failure.
1 out of 3	Enter at least 3 more patients at this dose level. If 0 of these 3 patients experience DLT, proceed to the next dose level. In the event that enrollment is on dose level 3 when this occurs, then dose level 3 is considered the MTD and the RP2D.
1 out of 3	If 1 or more of this group suffer DLT, then dose escalation is stopped, and this dose is declared the maximally administered dose. Three (3) additional patients will be entered at the next lowest dose level if only 3 patients were treated previously at that dose.

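### Section 9.3.3 gives idasanutlin doses of 300–500 mg a day, while the dose rationale and every dose table plan 50–200 mg

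*Combined protocol and SAP*

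**What the plan says.** Section 9.3.3, on idasanutlin dosage and storage, reads "The dose levels of Idasanutlin to be tested in this study are 300 - 500 mg PO by self-administration daily", on days 1–5 of a 28-day cycle. It does not say which formulation the figures refer to.

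The rest of the protocol gives a different and mutually consistent range:

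- Section 3.7.2.7 (dose rationale): "the doses tested in this study will range from 50 - 200 mg from D1 - 5 of each 28-day cycle". The same paragraph says that ongoing and future studies use the SDP formulation, at 50% of the older MBP dose, and that "the MTD for solid tumors on the 5 day schedule was 500 mg daily on the original formulation, and 250 mg of the current" SDP formulation.
- Section 7.4 (treatment table): levels −1, 1, 2 and 3 at 50, 100, 150 and 200 mg.
- Section 8.5 (idasanutlin reductions): steps of 200, 150, 100 and 50 mg, then discontinuation.
- Section 24.1 (Phase Ib): the same four levels. It ends escalation at 200 mg: "If dose level 3 is reached without DLT, then dose level 3 will be considered the MTD and RP2D".

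Section 7.6 fixes the start: "The first cohort of patients (3 patients) will be started at dose level 1". The tables in 7.4 and 24.1 put that level at 100 mg. Section 9.3.2, immediately before the disputed sentence, describes only "film-coated tablets with idasanutlin (SDP) that have been optimized for use in current and future studies", in strengths of 50, 200, 300 and 400 mg.

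**The concern.** Two statements of what will be tested cannot both be right, and the odd one out sits under a dosage heading for a self-administered investigational drug in a multicenter trial. A pharmacist who reads 9.3.2 and 9.3.3 together would take 300–500 mg as SDP doses. The listed 300 mg and 400 mg tablets make that range look plausible.

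The agent-specific section would not correct the impression, because 7.4.3 says only "Patients will receive and self-administer Idasanutlin at (TBD) mg PO daily". That placeholder is legitimate, since Phase Ib sets the final dose, but it offers no figure to check against.

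The protocol's own safety data show that overdosing would matter. In the earlier solid-tumor study, 11 of 34 patients (32%) on the 5-day daily schedule had a dose-limiting toxicity (3.7.2.3), and 13 of 34 (38.2%) had a related serious adverse event (3.7.2.5).

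**Working it through.** **Inputs.** Disputed range 300–500 mg (9.3.3). Planned levels 50, 100, 150 and 200 mg (7.4, 8.5, 24.1; range in 3.7.2.7). Conversion: SDP dose = 0.5 × older-formulation dose (3.7.2.7). MTD on the 5-day schedule: 500 mg original, 250 mg SDP (3.7.2.7).

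**Step 1: reproduce the stated MTD conversion.** 0.5 × 500 = 250 mg SDP, which agrees with 3.7.2.7.

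**Step 2: read 9.3.3 as SDP.** None of 50, 100, 150 or 200 mg falls within 300–500 mg. The ratios are:

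| Reference dose (SDP) | 300 mg | 500 mg |
|---|---|---|
| Stated MTD, 250 mg | 300/250 = 1.2 | 500/250 = 2.0 |
| Top planned level, 200 mg | 300/200 = 1.5 | 500/200 = 2.5 |
| Starting level, 100 mg | 300/100 = 3.0 | 500/100 = 5.0 |

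The whole range is above the MTD.

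**Step 3: read 9.3.3 as the older formulation.** 0.5 × 300 = 150 mg and 0.5 × 500 = 250 mg, so the range is 150–250 mg SDP.

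- Against the MTD: 150/250 = 0.6 to 250/250 = 1.0, so it is not exceeded.
- Against the plan: levels 2 (150 mg) and 3 (200 mg) fall inside. Level 1 (100 mg, the starting dose) and level −1 (50 mg) fall outside.
- At the top: 250 mg is not a planned level and is 250/200 = 1.25 times the planned maximum.

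**Step 4: run the conversion the other way.** If 9.3.3 were meant to state the plan in older-formulation terms, it would read 50/0.5 = 100 mg to 200/0.5 = 400 mg, or 200–400 mg for levels 1 to 3. It gives 300–500 mg, which is neither.

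**Step 5: compare the sister sentences in Section 9.** For cobimetinib, 9.2.2 says "The dose level of Cobimetinib to be tested in this study is 60 mg PO by self-administration daily", which matches 7.4.2. For atezolizumab, 9.4.3 gives 840 mg every two weeks, which matches 7.4.1. Only the idasanutlin sentence departs from the treatment plan.

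**The case against.** The strongest reply is that 9.3.3 does not govern dosing. It belongs to the formulation, storage and supply section and assigns no dose to any cohort. The sections that do (7.4, 7.6, 8.5 and 24.1) agree with one another and with the rationale in 3.7.2.7. Registration runs centrally through the coordinating center. This stands as far as it goes: a careful site would probably dose correctly, and nothing in the documents shows that a patient would be dosed from 9.3.3 alone. It lowers the likelihood of harm but does not make the sentence correct.

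A second reply is that the range may be left over from the older formulation. Its upper end equals the original-formulation MTD of 500 mg, and after conversion it includes two of the three escalation levels without exceeding the MTD. That origin is possible, though the documents do not confirm it. It would explain the text without rescuing it: the starting dose is still missing, and 250 mg is still unplanned. The multiples of the MTD in Step 2 apply only to the SDP reading, which 9.3.2 makes the natural one.

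It is also fair that leaving out 50 mg counts for less than leaving out 100 mg. Level −1 is used only if level 1 proves too toxic, although 3.7.2.7 does include it in the range.

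**Conclusion.** The concern holds. Section 9.3.3 contradicts four consistent statements of the idasanutlin dose, and neither formulation reading brings it into line. As most readers would take it (SDP), it describes doses 1.2–2.0 times the protocol's own stated MTD and 1.5–2.5 times the highest planned level. As older-formulation doses it would be 150–250 mg SDP, with a top dose 1.25 times the planned maximum.

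Two assumptions underlie these figures: the 50% conversion in 3.7.2.7, and the 250 mg MTD, which was not established for the combination with atezolizumab. The contradiction itself depends on neither.

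This is an internal inconsistency, and no design decision is in question. The levels in 7.4 and 24.1 remain defined, and sample size, error rates and power do not change. It must still be corrected, because a wrong dose for an investigational drug should not stay in the current protocol.

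**What to change.** Replace the 9.3.3 sentence with one that names the formulation and follows the tables, for example:

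> Idasanutlin (SDP formulation) is taken by mouth once daily on Days 1–5 of each 28-day cycle. The Phase Ib levels are 100, 150 and 200 mg (levels 1, 2 and 3), with 50 mg (level −1) if level 1 is not tolerated; see Sections 7.4 and 24.1. Phase II uses the RP2D.

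The investigators should confirm that 300–500 mg is erroneous text, and any site pharmacy documents should be checked against the corrected levels.

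The cost is a one-sentence amendment and that check. Design, sample size and analysis are unchanged.
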